3. STUDY DESIGN

Multi-center, prospective, randomized, open-label, pilot study

ARM 1: LDV/SOF x 12 weeks

ARM 2: LDV/SOF + RBV x 12 weeks

Number subjects:

Multi-center

50 subjects, with 25 subjects in each arm

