5. STUDY INTERVENTIONS

5.1 Interventions, Administration, and Duration

i. **SOF/LDV administration**

At the time of randomization, all subjects will be initiated on SOF/LDV 400mg/90mg enterally daily either with food or on an empty stomach. This medication will be administered predominantly outpatient, although it may be started or continued on both general hospital floors as well as the ICU. The medication will be continued for 12 weeks in both arms.

ii. **Ribavirin administration**

At the time of randomization, subjects in Arm 2 will be initiated on the appropriate weight-based dose to be taken with food. Subjects < 75kg will be initiated on RBV 400mg enterally in the morning (QAM) and 600mg enterally at night (QPM). Subjects \geq 75kg will be initiated on RBV 600mg enterally in the morning and night (BID).

This medication will be administered predominantly outpatient, although it may be started or continued on both general hospital floors as well as the ICU.

Ribavirin dosing may be adjusted as medically required for toxicity (see section iii).

iii. **Dosage adjustment of ribavirin**

Laboratory Abnormality	Reduction in current ribavirin dose
Hgb 8.5 to <10 g/dL and/or decrease by > 2 g/dL within 4 weeks	1. Decrease dose to 600mg daily (200mg QAM, 400mg QPM) 2. If Hgb < 12 g/dL despite 4 weeks of dose reduction in subjects with a history of stable cardiac disease, discontinue ribavirin
Hgb <8.5 g/dL	Discontinue ribavirin
WBC <1000 mm³ and/or ANC <500 mm³	Discontinue ribavirin
Platelets < 25 k/mm³	Discontinue ribavirin
eGFR 30-50 ml/min	Alternating doses, 200mg and 400mg every other day

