Gastrointestinal disorders	Diarrhea	1 - Increase of < 4 stools per day over baseline; mild increase in ostomy output compared to baseline	Grade 3 if requested by study participant, treatment-resistant or recurrent; Grade 4 or 5	Intervention can be withheld for up to 5 days. If there is no resolution, the case will be discussed with the medical monitor and the intervention may be discontinued. Grade 5: Intervention will be permanently discontinued
		2 - Increase of 4-6 stools per day over baseline; moderate increase in ostomy output compared to baseline		
		3 - Increase of ≥ 7 stools per day over baseline; incontinence; hospitalization indicated; severe increase in ostomy output compared to baseline; limiting self care ADL		
		4 - Life-threatening consequences; urgent intervention indicated		
		5 - Death		
Psychiatric disorders	Insomnia	1 - Mild difficulty falling asleep, staying asleep or waking up early	If requested by study participant	Intervention can be withheld for up to 5 days. If there is no resolution, the case will be discussed with the medical monitor and the intervention may be discontinued.
		2 - Moderate difficulty falling asleep, staying asleep or waking up early		
		3 - Severe difficulty in falling asleep, staying asleep or waking up early		
Musculoskeletal and connective tissue disorders	Arthralgia	1 - Mild pain	Grade 3 or if requested by study participant	Intervention can be withheld for up to 5 days. If there is no resolution, the case will be discussed with the medical monitor and the intervention may be discontinued.
		2 - Moderate pain; limiting instrumental ADL		
		3 - Severe pain; limiting self care ADL		

Renal and urinary disorders	Chronic kidney disease	1 - CrCl < LLN-60ml/min/1.73m ² ; proteinuria 2+ present; urine protein/creatinine > 0.5	Grade 2	Sofosbuvir/Ledipasvir to be held if CrCl <40ml/min/1.73m ² . Intervention can be withheld for up to 5 days. If there is no resolution, the case will be discussed with the medical monitor and the intervention may be discontinued. Ribavirin dose should be reduced to alternating doses of 200mg and 400mg every other day if CrCl 30-50ml/min/1.73m ² Interventions can be withheld for up to 5 days. If there is no resolution, the case will be discussed with the medical monitor and the intervention may be discontinued. Grade 5: Intervention will be permanently discontinued
		2 - CrCl 59-30m/min/1.73m ²		
		3 - CrCl 29-15ml/min/1.73m ²	Grade 3-5	
		4 - < 15ml/min/1.73m ² ; dialysis indicated		

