8. CRITERIA FOR INTERVENTION DISCONTINUATION

The intervention will be withheld/discontinued for specific grades of adverse effects as detailed in section 7. Additionally, the intervention will be discontinued if the subject meets criteria for the following reasons:

Virologic failure, defined as:

Breakthrough: HCV RNA \geq LLOQ after having previously had HCV RNA $<$ LLOQ, while on treatment, confirmed with 2 consecutive values (note: second confirmation value can be posttreatment), or last available on-treatment measurement with no subsequent follow up values, OR

Rebound: > 1 log₁₀IU/mL increase in HCV RNA from nadir while on treatment, confirmed with 2 consecutive values (note: second confirmation value can be post-treatment), or last available on-treatment measurement with no subsequent follow up values, OR

Nonresponse: HCV RNA persistently \geq LLOQ through 8 weeks of treatment, OR

Relapse: HCV RNA \geq LLOQ during the posttreatment period having achieved HCV RNA $<$ LLOQ at end of treatment, confirmed with 2 consecutive values or last available posttreatment measurement

Pregnancy: If a woman becomes pregnant or a male's female partner becomes pregnant while on-study, the subject will be required to instruct investigators immediately. If he/she is in Arm 1, he/she may remain on therapy but will be ineligible for treatment with ribavirin in the event of virologic failure. If he/she is in Arm 2, therapy must be discontinued immediately and the subject will be counseled on the potential risks of exposure by the PI or designee. A discussion will occur with the medical monitor to decide whether the subject is eligible to be continued on sofosbuvir/ledipasvir alone.

Loss of graft: Defined as death or need for retransplant. Patients will be deemed a treatment failure and the intervention will be discontinued.

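### At creatinine clearance 30 to below 40, the renal rules read literally leave an Arm 2 subject on reduced ribavirin without LDV/SOF, and no text says how ribavirin is then handled

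*Combined protocol and SAP*

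**What the plan says.** Section 3 defines two regimens: LDV/SOF in Arm 1, and "ARM 2: LDV/SOF + RBV x 12 weeks".

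In Section 7, the chronic kidney disease row sits in the table of adverse events common to both drugs. Its Grade 2 band is "2 - CrCl 59-30m/min/1.73m", and Grade 2 triggers modification. Within that row:

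- for LDV/SOF: "Sofosbuvir/Ledipasvir to be held if CrCl <40ml/min/1.73m";
- for ribavirin: "Ribavirin dose should be reduced to alternating doses of 200mg and 400mg every other day if CrCl 30-50ml/min/1.73m";
- in general: "Intervention can be withheld for up to 5 days. If there is no resolution, the case will be discussed with the medical monitor", after which the intervention may be discontinued.

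The ribavirin table in Section 5.1.iii has a matching line. The trigger is "eGFR 30-50 ml/min" and the action is "Alternating doses, 200mg and 400mg every other day". It sets no condition that LDV/SOF is still being given.

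The plan does cover the opposite situation, in which ribavirin stops and LDV/SOF goes on or may go on. In the Section 7 anemia row, a subject with Grade 3 or 4 anemia stops ribavirin permanently but carries on with the study intervention. For pregnancy in Arm 2, Section 8 says: "A discussion will occur with the medical monitor to decide whether the subject is eligible to be continued on sofosbuvir/ledipasvir alone".

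**The concern.** The two drug-specific rules have different cut-offs and neither mentions the other drug. In the range where both apply, LDV/SOF is off and ribavirin is on. The protocol does not set out to study that combination, and its background section offers no support for it. Section 2.1 describes ribavirin as poorly tolerated after transplant, and removing it is the reason for the trial. A subject in this range would carry ribavirin exposure without the antivirals it is meant to accompany.

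There is also a data-quality cost. Dose reduction, temporary withdrawal and removal of study drug are tolerability outcomes (Sections 9.2.3 and 9.7.1). In a multi-center, open-label trial, one site may withhold both drugs while another withholds one and reduces the other. The same renal event would then be recorded as different tolerability events.

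**Working it through.** No sample size or power figure is involved. The check is to apply the stated thresholds and see which combination of drugs results.

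**Inputs.** LDV/SOF is held below 40 and ribavirin is reduced at 30-50 (both Section 7). The reduction is repeated at eGFR 30-50 (Section 5.1.iii). Grade 2 covers 30-59 (Section 7). Entry requires at least 40 by Cockcroft-Gault (Section 4.1).

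**Overlap.** {CrCl < 40} and {30 ≤ CrCl ≤ 50} together give 30 ≤ CrCl < 40, all of it within Grade 2.

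| CrCl | LDV/SOF | Ribavirin in Arm 2 | Net result in Arm 2 |
|---|---|---|---|
| above 50 | given | no renal reduction stated | LDV/SOF + ribavirin |
| 40 to 50 | given | reduced | LDV/SOF + reduced ribavirin |
| 30 to below 40 | held | reduced | reduced ribavirin alone |
| below 30 | held (the rule has no lower limit) | may be withheld (text that appears to belong to Grade 3-5) | left to site and medical monitor |

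Only the third line produces, by stated rules, a regimen that is in neither arm.

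**Does other text resolve it?**

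- *The general withholding sentence.* It says what a site can do, whereas the ribavirin sentence says what should be done. It also depends on what *intervention* means. Section 5 lists both drugs as study interventions, which suggests the whole regimen. The anemia row has the subject continue the study intervention after ribavirin is permanently stopped, so there the word excludes ribavirin. Both readings have support.
- *Section 6.2.3.* It arranges a visit within 72 hours of premature termination, but does not separate the two drugs.
- *Section 8 and the anemia row.* They deal only with ribavirin stopping first.

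None of these says how ribavirin is handled while LDV/SOF is held or after it is discontinued.

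**Duration.** The hold runs for up to 5 days and then goes to the medical monitor. The literal reading therefore gives a ribavirin-only period of up to 5 days before review. What follows is not stated.

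**Scale of measurement.** Entry uses Cockcroft-Gault in ml/min, Section 5.1.iii uses eGFR in ml/min, and Section 7 uses CrCl per 1.73 m². These are not interchangeable. As an illustration, suppose a site indexes a Cockcroft-Gault value of 42 ml/min to body surface area (BSA), which the documents do not give:

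- at an assumed BSA of 1.73 m², 42 × 1.73 / 1.73 = 42.0, above the hold threshold;
- at an assumed BSA of 2.0 m², 42 × 1.73 / 2.0 = 36.3, inside the overlap;
- the result falls below 40 once BSA exceeds 42 × 1.73 / 40 = 1.82 m².

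The same eligible subject can therefore be in or out of the band with no change in renal function.

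**The case against.** The strongest reply is that no sentence tells a site to give ribavirin alone. That result comes from combining two rules, each written for one drug. The row is in the table common to both drugs, so *intervention* can fairly be read as the whole Arm 2 regimen. The site may then withhold ribavirin too, and the medical monitor sees any unresolved case after at most 5 days. This stands in part. The site has discretion, and it would be too strong to say that the protocol directs ribavirin monotherapy. But the discretion rests on an undefined word that the anemia row uses in the other sense, and the ribavirin instruction is the more specific of the two.

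It can also be said that this is an estimation pilot, that intent-to-treat keeps modified subjects by design, and that dose changes are themselves outcomes. That is right, and it limits the effect on the efficacy comparison. It does not remove the need for sites to apply one rule.

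A reader might infer four stronger points, which the documents do not support:

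- *Ribavirin alone for the rest of the 12 weeks.* This would need LDV/SOF to be discontinued and ribavirin left running after the medical monitor's review. The text is silent on that; it does not provide for it.
- *Rules that become softer as renal function worsens.* The LDV/SOF hold has no lower limit, so it still applies below 30. Moving ribavirin from reduction to possible withholding is not softer. The split of this cell between grades is also uncertain in the extracted table.
- *A subject entering at 42 needs to lose only 3 ml/min.* The entry value and the hold threshold are on different scales and cannot be subtracted.
- *Each case costs 4 percentage points of Arm 2 SVR12 (1/25).* The LDV/SOF hold applies in both arms whether or not ribavirin continues, and nothing in the documents says that a hold of up to 5 days changes SVR12. The figure does not measure this defect.

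**Conclusion.** The point holds as an internal gap between dosing rules. From CrCl 30 to below 40, the Section 7 rules followed as written leave an Arm 2 subject on reduced ribavirin without LDV/SOF, a regimen in neither arm, at least until the medical monitor discussion after a hold of up to 5 days. The plan does not state how ribavirin is handled during that hold or if LDV/SOF is then discontinued. The differing renal measures add uncertainty about who falls in the band.

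This rests on reading the two drug-specific sentences literally and on taking the withholding sentence as permissive. It does not depend on how the Grade 3-5 text is assigned within the row. The number of subjects affected cannot be estimated, because the documents give no expected rate of renal decline. The matter should be corrected for subject safety and for consistent tolerability data. It is not shown to threaten the SVR12 estimate.

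**What to change.** Reconcile the chronic kidney disease row of Section 7 with the renal line of Section 5.1.iii so that they:

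1. state what happens to ribavirin in Arm 2 whenever LDV/SOF is held for renal function, and whenever it is then discontinued;
2. define *intervention* in the row, so that it is clear whether the withholding sentence covers one drug or both;
3. use one renal measure, with one unit, for entry, ribavirin adjustment and the LDV/SOF hold.

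The clinical rule itself is for the sponsor and medical monitor to choose. The cost is an amendment of a few sentences, with no added subjects or study procedures.

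### The ribavirin renal instruction becomes less directive below a clearance of 30 ml/min, and the same table row words the LDV/SOF hold below 40 in two ways

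*Combined protocol and SAP*

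**What the plan says.** Two places give renal instructions for ribavirin.

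- The dose-adjustment table in Section 5.1.iii has one renal row. Its trigger is "eGFR 30-50 ml/min" and its action is "Alternating doses, 200mg and 400mg every other day". There is no row below 30.
- The chronic kidney disease row of Section 7 says "Ribavirin dose should be reduced to alternating doses of 200mg and 400mg every other day if CrCl 30-50ml/min/1.73m".

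The Section 7 row separates Grade 2 (clearance 59-30) from Grades 3-5 as criteria for modification. Grade 3 is given as "3 - CrCl 29-15ml/min/1.73m", Grade 4 is below 15 or dialysis, and Grade 5 is death. After the ribavirin reduction, the row continues "Interventions can be withheld for up to 5 days". Should the problem persist beyond that, the next step is a compulsory conversation with the medical monitor, after which stopping is optional. Only Grade 5 carries a compulsory permanent stop.

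For LDV/SOF the same row says "Sofosbuvir/Ledipasvir to be held if CrCl <40ml/min/1.73m", with no lower limit. A permissive sentence allowing up to 5 days of withholding follows immediately.

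**The concern.** A safety rule graded by severity should not become less definite as severity rises. Here a site is told what to do with ribavirin at a clearance of 30-50, but at 15-29 or on dialysis it is left with options.

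The protocol handles other ribavirin toxicities differently. In Section 5.1.iii, hemoglobin moves from a dose reduction to discontinuation as it falls. In Section 7, anemia and hemolysis at Grades 3-5 lead to a compulsory permanent stop. The kidney row runs the other way.

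Two things are at stake. The first is the safety of an Arm 2 subject whose clearance falls past 30 without a reduction already in place. The second is consistency of the data: dose reduction, temporary withdrawal and removal of study drug are themselves safety outcomes (Sections 9.2.3 and 9.7.1), so sites that read the row differently will generate different event counts for the same clinical course.

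**Working it through.** The plan states no figure to reproduce on this point. The check traces the written rules by clearance band and then sizes the dose difference. Section 5.1.iii uses eGFR in ml/min, Section 7 uses clearance per 1.73 m², and the entry criterion uses Cockcroft-Gault in ml/min. I treat these as one scale for the comparison.

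**Instructions by band**

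| Clearance | Ribavirin | LDV/SOF |
|---|---|---|
| Above 50 | No reduction directed | No hold directed |
| 40-50 | Reduction directed (5.1.iii and Section 7) | No hold directed |
| 30-39 | Reduction directed (both) | Hold stated, followed by permissive withholding |
| 15-29 (Grade 3) | No reduction or stop directed; withholding and discontinuation optional | Hold threshold still met; permissive text also present |
| Below 15 or dialysis (Grade 4) | As Grade 3 | As Grade 3 |
| Death (Grade 5) | Stop | Stop |

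The ribavirin column does not depend on where the table's cell boundaries fall. The lower limit of 30 is explicit in both sections, and neither gives a ribavirin directive below it.

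**Dose difference**

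- Starting dose (Section 5.1.ii): 400 + 600 = 1000 mg/day below 75 kg; 600 + 600 = 1200 mg/day at 75 kg or more.
- Reduced dose at 30-50, if 200 mg and 400 mg are taken on alternate days: (200 + 400)/2 = 300 mg/day.
- Ratio: 1000/300 = 3.3 and 1200/300 = 4.0.
- If the wording instead means one dose every second day, the average is 150 mg/day and the ratios are 1000/150 = 6.7 and 1200/150 = 8.0.

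**How a subject could be below 30 without a reduction**

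- A subject observed at 30-50 should already have been reduced, and nothing directs a return to the higher dose. The route is therefore an unobserved fall from above 50 to below 30, or a missed reduction.
- On treatment, the schedule in Section 6.1 requires laboratory assessments at weeks 4, 8 and 12 only. Baseline evaluations may be up to 14 days old at randomization (Section 6.2.1) and the week 4 window extends to day 33 (28 + 5). The first gap between required checks can thus reach 14 + 33 = 47 days.
- Cockcroft-Gault clearance is inversely proportional to creatinine. A fall from 55 to 29 needs a creatinine rise of 55/29 = 1.9-fold; from 60 to 29, 60/29 = 2.1-fold.
- Entry is allowed from 40, and Section 5.1.ii sets the starting dose by weight alone. If a subject at 40-50 were started on the weight-based dose without the reduction, reaching 29 needs only 40/29 = 1.4-fold to 50/29 = 1.7-fold.

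The documents give no rate of renal decline, so the number of subjects affected cannot be calculated.

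**The case against.** The strongest reply is that the protocol relies on judgment here by design. Section 7 uses the same sequence of optional withholding, monitor discussion and optional discontinuation for other serious events, including hepatic failure and anaphylaxis. The discussion with the medical monitor is compulsory if there is no resolution. Section 5.1.ii also lets ribavirin be adjusted as medically required for toxicity, the required laboratory checks are a minimum, and the Section 7 reduction is itself worded as something that should be done. All of this stands, and it makes harm less likely. It does not explain why the milder renal band needed a directive and the worse bands did not.

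A reader might infer that the LDV/SOF hold lapses below 30. The documents do not support that. The threshold of below 40 has no lower bound and so covers 29, 15 and dialysis. The permissive withholding sentence also follows the hold directly, so the tension exists at every value below 40. Confining the hold to Grade 2 would depend on a cell boundary that the extracted table does not show.

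A reader might also infer that subjects with severe renal impairment would routinely stay on full-dose ribavirin. That is not supported either. It needs the unobserved fall or missed reduction described above, and then a site that uses neither the withholding option nor the toxicity clause.

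**Conclusion.** The point holds for ribavirin. Both renal rules direct a reduction at 30-50 only, and for Grades 3 and 4 nothing is directed short of discussion with the medical monitor. The written instruction becomes less directive as renal function worsens.

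The exposed group is Arm 2, 25 planned subjects, and within it only those who reach a clearance below 30 without an earlier reduction. For them the dose not subject to any directed change is 3.3 to 4.0 times the average directed at 30-50, assuming daily alternation. This ratio compares doses on a worst-case path; it is not an expected effect, and no count of affected subjects or consequence for SVR12 can be derived.

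For LDV/SOF the conclusion is narrower: the row contains a firm and a permissive instruction for values below 40 and does not make clear which governs, including at Grades 3 and 4.

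**What to change.** Reconcile Section 5.1.iii with the chronic kidney disease row of Section 7 so that each clearance band, down to and including dialysis, carries one unambiguous instruction for ribavirin and one for LDV/SOF. Make clear which procedure text belongs to Grade 2 and which to Grades 3-5, and use one named renal measure in both places. The content of each instruction is for the clinical team to set; none is proposed here.

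The cost is a small text edit in two tables, with no added visits or subjects.

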		5 - Death		
Investigations	Blood bilirubin increased	1 - >ULN - 1.5x ULN	Grade 3-4	Intervention can be withheld for up to 5 days. If there is no resolution, the case will be discussed with the medical monitor and the intervention may be discontinued.
		2 - >1.5-3x ULN		
		3 - >3-10x ULN		
		4 - >10x ULN		
Investigations	Lipase increased	1 - > ULN-1.5x ULN	Grade 3-4	Intervention can be withheld for up to 5 days. If there is no resolution, the case will be discussed with the medical monitor and the intervention may be discontinued.
		2 - >1.5-2x ULN		
		3 - >2-5x ULN		
		4 - >5x ULN		

Ribavirin

CTCAE SOC	Adverse Event	Grade Description	Criteria for Modification of Intervention	Procedure for Modification
Blood and lymphatic system disorders	Anemia	1 - Hgb <LLN-10g/dL	Grade 2, modifications to dosage	Grade 2: see dosage adjustment procedure in section 5.1.iii
		2 - Hgb <10-8g/dL		
		3 - < 8g/dL	Grade 3-5: permanently discontinue ribavirin	Grade 3-5: ribavirin will be permanently discontinued. Subject experiencing Grade 3 or 4 will continue the study intervention and follow study
		4 - Life-threatening consequences; urgent intervention indicated		

		5 – Death		evaluations as detailed in section 6.1
Blood and lymphatic system disorders	Hemolysis	1 – Laboratory evidence of hemolysis only (e.g. DAT, Coombs', schistocytes, decreased haptoglobin)	Grade 2: modifications to dosage Grade 3-5: permanently discontinued	Grade 2: see dosage adjustment procedure in section 5.1.iii Grade 3-5: intervention will be permanently discontinued.
		2 – Evidence of hemolysis and $\geq 2g/dL$ decrease in Hgb		
		3 – Transfusion or medical intervention indicated		
		4 – Life-threatening consequences; urgent intervention indicated		
		5 – Death		
Hepatobiliary disorders	Hepatic failure	3 – Asterixis; mild encephalopathy; limiting self care ADL	Grade 3-5	Intervention can be withheld for up to 5 days. If there is no resolution, the case will be discussed with the medical monitor and the intervention may be discontinued. Grade 5: Intervention will be permanently discontinued
		4 – Moderate to severe encephalopathy; coma; life-threatening consequences		
		5 – Death		

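### The Section 7 Ribavirin table stops only ribavirin for Grade 3-5 anemia but an undefined intervention for Grade 3-5 hemolysis, so it is unclear whether LDV/SOF continues in Arm 2

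*Combined protocol and SAP*

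**What the plan says.** The Ribavirin table in Section 7 has adjacent rows for anemia and hemolysis.

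- **Anemia.** The criteria column reads "Grade 3-5: permanently discontinue ribavirin". The procedure column reads "Grade 3-5: ribavirin will be permanently discontinued. Subject experiencing Grade 3 or 4 will continue the study intervention and follow study" evaluations, with a reference to Section 6.1.
- **Hemolysis.** Grade 3 is defined as "Transfusion or medical intervention indicated". The procedure for the upper grades is "Grade 3-5: intervention will be permanently discontinued". No drug is named, and no sentence says what continues.
- **Both rows** treat the grade below in the same way: "Grade 2: see dosage adjustment procedure in section 5.1.iii". That section is a dose table for ribavirin alone, and its hematologic stopping rows say to "discontinue ribavirin".

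Section 8 makes this wording operative: "The intervention will be withheld/discontinued for specific grades of adverse effects as detailed in section 7". Section 5.1, on the study interventions, covers both LDV/SOF and ribavirin and plans 12 weeks of LDV/SOF in both arms. No section defines *intervention*.

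**The concern.** The two rows overlap. Hemolysis Grade 2 already includes a hemoglobin fall of at least 2 g/dL, and Grade 3 is reached when a transfusion is indicated. One subject can therefore meet both rows at once. The anemia row then tells the site to carry on with LDV/SOF, while the hemolysis row can be read as stopping it for good.

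Two things are at stake. The first is safety: sites lack a single instruction for a serious event. The second is the estimate. Only Arm 2 receives ribavirin, and Section 9.4.2 keeps every randomized subject in the assigned arm. If LDV/SOF is cut short for a ribavirin toxicity, any loss of SVR12 falls on Arm 2, the reference arm in Section 9.4.1. That would make the ribavirin-free arm look better for a procedural reason. Section 9.3 says that the pilot's rates are meant to feed a definitive trial.

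**Working it through.** **1. The plan's own figure.** The point rests on no stated figure. For completeness, the 75 per arm in Section 9.3 reproduces from 95% in both arms, a margin of 0.10 and 80% power:

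n = (1.960 + 0.842)² × 2 × 0.95 × 0.05 / 0.10² = 7.85 × 9.5 = 74.6, rounded up to 75.

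The stated alpha of 0.05 thus acts as two-sided. Clarifying the table does not change this number.

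**2. The instructions side by side.**

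| Place | Trigger | What is stopped | What is said of LDV/SOF |
|---|---|---|---|
| Section 5.1.iii | Hgb below 8.5 g/dL | Ribavirin | Nothing |
| Section 7, anemia | Grade 3: Hgb below 8 g/dL | Ribavirin | Continues at Grade 3 or 4, on the only workable reading |
| Section 7, hemolysis | Grade 3: "Transfusion or medical intervention indicated" | Intervention, permanently | Nothing, unless it is the intervention |

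A subject with hemolysis, Hgb below 8 g/dL and an indicated transfusion meets all three.

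**3. The two readings of the hemolysis row.**

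- *Intervention includes LDV/SOF.* This follows the usage one row above. If the word meant ribavirin there, the anemia row would stop and continue ribavirin in the same breath.
- *Intervention means ribavirin.* This follows the table heading and the row's own sequence, since its Grade 2 step points to a ribavirin-only dose table.

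No definition decides between them. Nor does the row contain a step at which a misreading would be caught. It is the only row in Section 7 that permanently stops the intervention at a survivable grade without first allowing a hold and a discussion with the medical monitor. The hepatic failure and anaphylaxis rows allow both at Grades 3 and 4.

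**4. Effect on the Arm 2 estimate.** Arm 2 has 25 subjects (Section 3). One subject turned from success to failure changes the proportion by 1/25 = 4 points.

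For the expected rate, let h be the share of Arm 2 whose LDV/SOF is stopped under the hemolysis row, and s the SVR12 rate in those subjects. With the plan's 95% for everyone else:

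Arm 2 SVR12 = 0.95 × (1 − h) + s × h

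The documents give neither h nor s, so the values below are assumptions.

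| h | s = 0 | s = 50% | s = 80% |
|---|---|---|---|
| 0 | 95.0% | 95.0% | 95.0% |
| 1 of 25 (4%) | 91.2% | 93.2% | 94.4% |
| 2 of 25 (8%) | 87.4% | 91.4% | 93.8% |

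The loss runs from nothing, through 0.6 points (one subject, s = 80%), to 7.6 points (two subjects, s = 0). Only Grades 3 and 4 matter here, because Grade 5 is death.

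**5. Scale.** At 95% in both arms and 25 per arm, the 95% confidence interval for the difference has a half-width of 1.96 × √(2 × 0.95 × 0.05 / 25) = 12.1 points. A shift of a few points would not be visible as bias in the pilot's results.

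**The case against.** The best case for the plan is that the hemolysis row is a single sequence. At Grade 2 the thing modified is the ribavirin dose, so the thing stopped at Grade 3 and above should be ribavirin too. The table heading supports this. Usage elsewhere also varies with context: the kidney row names each drug and uses the general word as well, and Section 8's pregnancy rule stops Arm 2 therapy and then leaves LDV/SOF alone to be decided. This stands as a plausible reading, and it is why the point is an ambiguity and not a proven order to stop LDV/SOF. It does not settle the matter, because the neighboring row uses the word for the opposite remainder.

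Existing text covers part of the remedy. The safety outcomes count removal of study drug or drugs, adverse event reports include the action taken, and early termination prompts a visit within 72 hours. None of these says which drug the hemolysis row stops, or requires stops to be recorded by drug.

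A reader might infer three stronger claims, and the documents support none of them:

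- *That hemolysis and anemia are the same event and usually meet both rows.* They are separate terms with different Grade 3 criteria, and no overlap rate is given.
- *That two or three such subjects, or 8 to 12 points, would offset the 10-point margin.* This assumes the event count, the broad reading each time, and failure in every subject who would otherwise have succeeded.
- *That a noninferiority conclusion could be tipped.* Section 9.4.2 says the pilot lacks the power for formal analysis, so no such decision is taken here.

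Other rows in the table, such as irritability, pruritus and dyspnea, use the same undefined word. At Grade 3, and at Grade 4 for dyspnea, they provide for a hold and a discussion, so they do not carry this conflict.

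**Conclusion.** The point holds as an unresolved ambiguity. For Grade 3 and 4 events the anemia row keeps LDV/SOF going, while the hemolysis row can be read as ending it. A subject who meets both may be managed differently from site to site.

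If LDV/SOF is stopped, the cost is 4 points on the Arm 2 estimate for each subject who loses an SVR12 they would otherwise have had, in the direction that favors LDV/SOF alone. This assumes that a site takes the broad reading and that stopping early causes the failure. The total cannot be sized from the documents, and it is zero if no such event occurs. The consequence is conflicting safety instructions and a possibly biased estimate passed to the definitive trial.

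**What to change.** Reconcile the anemia row, the hemolysis row and Section 5.1.iii so that one event leads to one stated action for each drug. In the Ribavirin table, replace *intervention* with the drug or drugs meant: ribavirin, LDV/SOF or both. The choice of action belongs to the sponsor's clinicians.

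Record holds and permanent stops separately for ribavirin and LDV/SOF, with the reason, so that any LDV/SOF stop made for a ribavirin toxicity can be identified beside the SVR12 results.

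The cost is a protocol clarification in one table and, if the case report form does not already separate the drugs, a small change to it. No patients, visits or procedures are added, and the sample size is unchanged.
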